4.3. Removal of Subjects From Therapy

4.3.1. Reasons for Withdrawal/Early Discontinuation

Any subject who discontinues from the study for any reason will have their study discontinuation recorded.

Subjects may be withdrawn from the study after signing informed consent for the following reasons:

- AE or SAE
- Lost to follow-up
- Withdrawal of consent by subject
- Physician decision

Study terminated by sponsor

Other

If a subject withdraws from the study, the Investigator will complete and report the observations as thoroughly as possible up to the date of withdrawal and the reason for withdrawal.

If the subject is withdrawn due to an AE, the Investigator will follow the subject until the AE has resolved or stabilized.

All subjects who are withdrawn from the study should complete protocol specified withdrawal procedures (Day 181).

4.3.2. Withdrawal Procedures

Subjects who withdraw from the study will be required to undergo Check-out/Early Termination procedures (Day 181). If a subject withdraws from the study prior to Day 29, they will be required to undergo Check-out/Early Termination procedures (Day 29).

If the subject is withdrawn due to an AE, the Investigator or designee will attempt to follow the subject until the AE has been resolved or stabilized. Whenever possible, withdrawn subjects will undergo End of Study (EoS) procedures after withdrawal and Follow-up. More follow-up safety assessments than those prescribed in this protocol may be ordered at the Investigator's or designee's discretion in subjects who are withdrawn due to an AE, but non-protocol assessments will not necessarily be included in the clinical database.

4.3.3. Subject Replacement

Subjects who discontinue will not be replaced unless approved by the Sponsor.

5. TREATMENTS ADMINISTERED

5.1 Investigational Products

Fluzone Intramuscular Quadrivalent vaccine is a marketed product, although for this study it is referred to as IP.

5.2. Method of Assigning Subjects to Treatments and Blinding

This is an open-label study. There is no blinding of study treatment.

5.3. Method of Assessing Treatment Compliance

To ensure treatment compliance, each intramuscular dose of vaccine will be administered delivered by a clinic staff member. The time and date the medication is given will be recorded in the CRF.

5.4. Labeling and Packaging

Fluzone Intramuscular Quadrivalent vaccine will be obtained from commercial sources. All prefilled single dose syringes will be labeled with the contents identified.

5.4.1. Preparation

No preparation of the study drug is required by a pharmacist.

The study drug will be administered in accordance with the protocol. Study drug will be administered only to subjects participating in the clinical study. It is a violation of the regulations to use unapproved study products for purposes other than stated in the protocol.

The site will complete the required documentation as provided by the Sponsor or its representatives to document dispensing of the product. All information will be recorded immediately on a drug dispensing form each time the study drug is dispensed to a subject.

5.4.2. Storage Conditions

Fluzone Intramuscular Quadrivalent vaccine is to be stored at 2°C to 8°C (35°F to 46°F) in a secure, limited access storage area.

In the event that storage conditions exceed the permissible temperatures, the Sponsor should be contacted within 24 hours of becoming aware of the incident.

5.4.3. Drug Accountability

When a drug shipment is received, the Investigator or designee will check the amount and condition of the drug, check for appropriate local language in the label, drug expiration date and sign the Receipt of Shipment Form provided. The Receipt of Shipment Form should be faxed as instructed on the form. The original will be retained at the site. In addition, the Investigator or designee shall contact the Sponsor as soon as possible if there is a problem with the shipment.

A Drug Accountability Record will be provided for the IP. The record must be kept current and should contain the dates and quantities of drug received, subject's (identification number and/or initials or supply number as applicable), for whom the IP was dispensed, the date and quantity of

IP dispensed and remaining, if from individual subject drug units as well as the initials of the dispenser.

At EoS, or as directed, all unused, partially used, or empty containers, will be returned to a designee as instructed by Sponsor. IP will be returned only after the study monitor has completed a final inventory to verify the quantity to be returned. The return of IP must be documented and the documentation included in the shipment. At EoS, a final IP reconciliation statement must be completed by the Investigator or designee and provided to the Sponsor. Unused drug supplies may be destroyed by the Investigator when approved in writing by Sponsor and Sponsor has received copies of the site's drug handling and disposition Standard Operating Procedures (SOPs).

All IP inventory forms must be made available for inspection by a Sponsor-authorized representative or designee and regulatory agency inspectors. The Investigator is responsible for the accountability of all used and unused study supplies at the site.

5.4.4. Retention Samples

No retention samples are required.

5.5. Concomitant Medications

Medications used within 30 days prior to Screening will be recorded. Receipt of any vaccine or the influenza vaccine within approximately 1 and 6 months, respectively, of enrollment in this study is exclusionary.

Use of any prescription or OTC medications (systemic or topical), vitamins, or dietary/herbal supplements will be permitted except those specified in Exclusion criteria or those deemed by the Investigator that could possibly interfere with the study.

Any immunosuppressive medication or vaccines (other than study drug administered) taken by subjects during the course of the study will be recorded and coded using the World Health Organization (WHO) dictionary. If drug therapy other than that specified by the protocol is taken, a joint decision will be made by the Investigator or designee and Sponsor whether to continue or discontinue the subject.

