I understand that the Sponsor may decide to suspend or prematurely terminate the study at any time for whatever reason; such a decision will be communicated to me in writing. Conversely, should I decide to withdraw from execution of the study, I will communicate my intention immediately in writing to the Sponsor.

_____ Print Name	_____ Signature
_____ Investigator Title	_____ Date (DD MMM YYYY)

PROTOCOL SYNOPSIS

Protocol Number:	ALT-FLZ-401
Product:	Fluzone Intramuscular Quadrivalent vaccine
Active Ingredient(s)/INN:	Vaccine
Study Title:	Extent and Durability of Immune Response Following Seasonal Influenza Vaccination in Healthy Volunteers
Study Phase:	Phase 4
Indication Under Investigation:	Influenza
Study Objectives:	
Primary Objective
 
To evaluate antibody response against matched influenza strains as measured by hemagglutination inhibition (HAI) following administration of a seasonal influenza vaccine.
 
Secondary Objectives
 
To evaluate 1) antibody responses to divergent influenza strains 2) cellular immune responses and 3) mucosal antibody responses following administration of seasonal influenza vaccine (Fluzone Quadrivalent)

Study Design:	
This will be an open-label, single administration dose study in adult healthy male and female subjects. After qualifying for the study, subjects will receive a single intramuscular injection of the FDA approved 2016-2017 quadrivalent influenza vaccine.
 
Subjects will be screened within 28 days prior to enrollment into the study. After qualifying for the study subjects will visit the clinical unit on Day 1 and will have pre-dose blood samples taken for humoral (serum) and cellular (peripheral blood mononuclear cells PBMCs) immunity testing and nasopharyngeal swabs for assessment of mucosal immunity, and will then be given the vaccine. Over the next 6 months, 10-mL blood samples will be collected on Days 4, 8, 15, 29, 91 and 181 for HAI testing. Peripheral blood mononuclear cells will be collected on Day 8 to assess cellular responses. A nasopharyngeal swab will also be done on Day 29. Screening assessments will include clinical laboratory tests (hematology, chemistry, urinalysis

	[UA], drug and alcohol testing), vital signs, 12-lead electrocardiogram and physical examination. Adverse events (AEs) will be monitored throughout the study.

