 26. Any medical, psychiatric, or social condition or any occupational or other responsibility that in the judgment of the Investigator would interfere with or serve as a contraindication to protocol adherence, assessment of safety (including immunogenicity), or a subject's ability to give informed consent
-

Dosage Form, Dose and Route of Administration:

- Solution dose (0.5 mL), intramuscular
-

Study Endpoints:

Efficacy (immunogenicity)

Antibody and cellular immune responses following seasonal influenza vaccination

Safety

AEs

Statistical Analyses:

Sample Size Determination

Based on practical considerations, 20 subjects will be enrolled.

Safety

For safety, the primary assessment will be adverse event rate, type of adverse event, severity.

TABLE OF CONTENTS

1.	INTRODUCTION.....	13
1.1	Study Rationale	13
1.2	Risks and Benefits for Study Subjects	13
1.3	Population, Route, Dosage, Dosage Regimen, Treatment Period.....	14
1.4	Compliance Statement, Ethics and Regulatory Compliance.....	14
1.4.1	Subject Confidentiality.....	14
1.4.2	Informed Consent Procedure.....	14
1.4.3	Regulatory Compliance.....	15
2.	STUDY OBJECTIVES	16
2.1.	Primary Objective.....	16
2.2.	Secondary Objectives	16
3.	STUDY DESIGN	17
3.1	Overall Plan.....	17
3.1.1.	Study Type	17
3.1.2.	Treatment Groups.....	17
3.1.3.	Study Endpoints	17
3.1.4.	Duration of the Study	17
3.1.5.	Duration of Subject Participation.....	17
3.2	Selection of Dose.....	17
4.	STUDY POPULATION.....	18
4.1	Enrollment	18
4.2	Inclusion and Exclusion Criteria	18
4.3	Removal of Subjects From Therapy.....	20
4.3.1.	Reasons for Withdrawal/Early Discontinuation.....	20
4.3.2.	Withdrawal Procedures	21
4.3.3.	Subject Replacement	21
5.	TREATMENTS ADMINISTERED.....	22
5.1	Investigational Products	22

5.2.	Method of Assigning Subjects to Treatments and Blinding.....	22
5.3.	Method of Assessing Treatment Compliance.....	22
5.4.	Labeling and Packaging	22
5.4.1.	Preparation.....	22
5.4.2.	Storage Conditions	22
5.4.3.	Drug Accountability	22
5.4.4.	Retention Samples	23
5.5.	Concomitant Medications.....	23
5.6.	Lifestyle Guidelines	23
6.	STUDY PROCEDURES.....	24
6.2	Randomization.....	24
6.3	Treatment Period	24
6.3.1	Day 1	24
6.4	End-of-Study	26
6.5	Follow-up	26
6.6	Protocol Deviations	26
7.	EFFICACY ASSESSMENTS	27
8.	IMMUNOGENECITY ASSESSMENTS	28
9.	PHARMACOKINETIC ASSESSMENTS..... ERROR! BOOKMARK NOT DEFINED.	
10.	SAFETY ASSESSMENTS	31
10.1.	Adverse Events.....	31
10.2.	Safety Variables	31
10.3.	Definitions	31

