7. Clinically significant ECG abnormality
8. Poorly controlled hypertension (systolic blood pressure $> 150 \text{ mmHg}$ or diastolic blood pressure $> 95 \text{ mmHg}$) at Screening or predose on Day 1
9. History of anaphylaxis or angioedema
10. Known allergy to any of the ingredients in the vaccine formulation, including egg allergy
11. History of chronic rhinitis, nasal septal defect, cleft palate, nasal polyps, or other nasal abnormality that might affect vaccine administration
12. Previous nasal surgery or nasal cauterization
13. Any symptoms of upper respiratory infection or temperature $> 38^\circ\text{C}$ within 3 days before Day 1
14. Significant nasal congestion or rhinorrhea as assessed by the investigator.

15. Known or suspected malignancy, excluding non-melanoma skin cancers and other early stage surgically excised malignancies that the Investigator considers to be exceedingly unlikely to recur
16. Immunocompromised individuals, including those who have used corticosteroids (including intranasal steroids), alkylating drugs, antimetabolites, radiation, immunomodulating biologics, or other immunomodulating therapies within 90 days before Day 1 or those who plan use during the study period
17. Use of statin medication within 30 days before Day 1 (including atorvastatin, fluvastatin, lovastatin, pravastatin, rosuvastatin, simvastatin, pitavastatin)
18. Receipt of intranasal medications (including over-the-counter medications) within 30 days before Day 1
19. Receipt of any IP within 30 days before Day 1
20. Receipt of any vaccine within 30 days before Day 1
21. Receipt of intranasal vaccine within 90 days before Day 1
22. Receipt of any influenza vaccine within 6 months before Day 1
23. Any change in medication for a chronic medical condition within 30 days before Day 1
24. Past regular use or current use of intranasal illicit drugs, or any illicit drug by any route
25. Use of tobacco products or electronic cigarettes within 30 days before Day 1, or smoking of any type, including marijuana
26. Any medical, psychiatric, or social condition or any occupational or other responsibility that in the judgment of the Investigator would interfere with or serve as a contraindication to protocol adherence, assessment of safety (including immunogenicity), or a subject's ability to give informed consent

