All AEs and medications will be recorded from signing of the informed consent form to Day 29. Thereafter to the end of the study, only MAEs, NCIs, SAEs, immunosuppressive medications (see list in Appendix 3), and vaccines will be recorded. Samples for clinical laboratory tests (hematology, serum chemistry, urinalysis) will be collected at Screening and on Days 8 and 29. A complete physical examination and vital signs will be performed at Screening and predose on Day 1, and targeted and symptom-driven physical examinations will be performed and vital signs measured 2 hours postdose and on Days 4, 8, 15, and 29. An electrocardiogram (ECG) will be performed at Screening and on Day 29. If a subject experiences acute symptoms compatible with adenoviral infection within 28 days after the NasoVAX/placebo dose, a sample will be collected for viral culture as clinically indicated.

One interim analysis of humoral immunogenicity data and safety data (including summaries of AE, reactogenicity, concomitant medications and vaccines, vital signs, ECG, and laboratory data and listing of any viral culture results) will be conducted when all data through the Day 29 visit is available and monitored for all subjects.

A complete schedule of procedures and assessments for study ALT-103-201 is in Table 4-2.

ALT-FLZ-401, Extent and Durability of Immune Response Following Seasonal Influenza Vaccination in Healthy Volunteers, was an open label study designed to generate an immunogenicity sample set similar to that of ALT-103-201 in subjects receiving a licensed influenza vaccine based on the same H1 strain (A/California 2009). The seasonal vaccine H1 component changed at the time of the ALT-103-201 study to A/Michigan, so it was logistically much easier to conduct this study non-contemporaneously with the seasonal vaccine licensed for use in 2016-17. The same site, entry criteria and schedule of assessments for immunogenicity were followed. Twenty subjects were enrolled and samples from this study were frozen and stored and then shipped to blinded laboratory for immunogenicity testing in parallel to the samples from ALT-103-201. The schedule of events for ALT-FLZ-401 is in Table 4-3.

Table 4-2. ALT-103-201 TIME AND EVENTS SCHEDULE

Study Visit	Screening	Dosing Period							Follow-up Period	
		Day 1		Day 2 ^a	Day 4	Day 8	Day 15	Day 29	Day 91	Day 181
Window (days)	Day -28 to Day -1	Predose	Postdose		± 1	± 1	± 1	± 3	± 10	± 10
Informed consent	X									
Demographics	X									

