- **Per-protocol (PP) Population:** All ALT-103-201 subjects in the Safety Population that received the assigned dose of the test article in accordance with the protocol; have HAI assay results on Days 1 and 29; and had no major protocol deviations affecting the primary immunogenicity outcomes as determined by the Sponsor prior to database lock. ALT-FLZ-401 subjects are included if they received the assigned dose of the test article in accordance with the protocol and have HAI assay results on Days 1 and 29. The PP Population is the primary population for immunogenicity analyses and will be presented regardless of whether subjects are excluded. The PP population will be analyzed as randomized.

SUMMIT ANALYTICAL

6 Analysis Variables

In what follows, variables to be analyzed have been grouped under the headings 6.1 to 6.4. Additional variables may be added as further drafts of the eCRF and this SAP are developed and/or as discussion unfolds concerning the usefulness of *derived* variables formulated using the information presented below.

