8.6 Immunogenicity Analysis

All immunogenicity analyses will be conducted on the PP Population. Analyses based on the ITT Population will be undertaken and presented only if >5% of subjects in any 1 dose group were excluded from the PP Population. Summaries and analysis will be completed by dose group and overall for subjects on an active NasoVAX dose.

The variables that will be analyzed, and the endpoints generated for each variable, are listed in Table 8-1:

Table 8-1. Immunogenicity Variables and Endpoints

Variable Name	GMT	GMR	SPR	SCR	Responder Rate	Geometric Mean SFUs	Compare to ALT-FLZ-401
A/California 2009 antibody level measured by HAI in serum	X	X	X	X			X
A/California 2009 antibody level measured by MN in serum	X	X			X		X
Cellular response to A/California 2009 peptides measured by enzyme-linked ELISpot in PBMCs					X	X	X
IgA antibody level measured by ELISA in nasopharyngeal swab	X	X					X
Antibody level measured by HAI in serum against the following nonrepresented strains: - A/Brisbane/59/2007 (H1 strain) - A/Saint-Petersburg/61/2015 (H1 strain) - A/New Jersey/76 (H1 strain) - A/Perth/16/2009 (H3 strain) - A/Vietnam/1203/2004XPR8 (H5 strain)	X	X			X		X
Antibody level measured by MN in serum against nonrepresented strains	X	X			X		X
Ad5 antibody levels in serum	X	X			X		

Note: Refer to Section 3 for descriptions of each endpoint.

Assay data will be tabulated by visit using the applicable endpoint(s) (e.g., GMT, GMR, or geometric mean SFUs) and their 95% CIs. Graphical representations of the longitudinal immune responses will also be given.

[figure not shown]
Analysis of covariance (ANCOVA) will be used in the analysis of the antibody levels at each post-baseline visit, with log-transformed antibody level as dependent variable, dose group as a factor, and baseline log-transformed level as a covariate. This model will be generated using SAS Proc Mixed with dose group in the CLASS statement and visit in the BY statement. Comparisons of post-baseline log-transformed antibody level will be conducted for each NasoVAX dose group against the placebo group and against the Fluzone group, if applicable. Least square (LS) means and 95% CI of the LS means of dose group, difference of LS means and 95% CI of the difference in LS means will be

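### The plan has no analysis rule for HAI samples taken after a non-study influenza vaccine, so a boosted late titer, mainly at Day 181, would count as persistence of the study vaccine

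*Protocol*

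**What the plan says.** **Sampling.** The protocol synopsis states that "10-mL blood samples will be collected on Days 4, 8, 15, 29, 91 and 181 for HAI testing". Days 91 and 181 are the only visits after Day 29. The study title names durability, and HAI response is the primary objective.

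**Vaccines before and during the study.** Exclusion criterion 22 in Protocol 4.2 reads "Receipt of any influenza vaccine within 6 months before Day 1"; like the other vaccine exclusions, it looks backward from Day 1. For follow-up, Protocol 5.5 says "Any immunosuppressive medication or vaccines (other than study drug administered) taken by subjects during the course of the study will be recorded and coded". The same section does not permit medications that the investigator judges might interfere with the study. If non-protocol drug therapy is taken, "a joint decision will be made by the Investigator or designee and Sponsor whether to continue or discontinue the subject".

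**Who is analysed.** SAP 5 (Per-protocol) says "ALT-FLZ-401 subjects are included if they received the assigned dose of the test article in accordance with the protocol and have HAI assay results"; the results required are those of Day 1 and Day 29. Exclusion for major deviations is written for ALT-103-201 subjects only, and SAP 8.3 states that deviations were not collected in ALT-FLZ-401.

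**What is analysed.** SAP 8.6: "Analysis of covariance (ANCOVA) will be used in the analysis of the antibody levels at each post-baseline visit". The model terms are dose group and baseline level. SAP 7.4.7 has additional treatments in its heading, but its text deals only with early-termination visits.

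**Season.** SAP 4 notes that "The seasonal vaccine H1 component changed at the time of the ALT-103-201 study to A/Michigan".

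**The concern.** A late HAI titer can be read as persistence of the study vaccine only if nothing else has raised it. A second influenza vaccine during follow-up may do so. The plan collects this information but makes no use of it in the immunogenicity analysis.

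If any Fluzone subject is re-vaccinated before Day 181, the visit-wise GMT, geometric mean ratio (GMR), seroprotection rate (SPR), seroconversion rate (SCR) and ANCOVA would attribute the combined effect to the study dose. Waning would look smaller than it is. The planned NasoVAX-versus-Fluzone contrasts at late visits would be shifted as well, in a direction that depends on which groups were re-vaccinated more often.

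**Working it through.** The plan gives no figure to reproduce here. The sample size has no precision basis ("Based on practical considerations, 20 subjects will be enrolled"). The check has three parts.

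**1. Does any rule remove the sample?** Take a Fluzone subject with valid Day 1 and Day 29 HAI who receives another influenza vaccine between Day 29 and Day 181.

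- *PP membership (SAP 5):* already settled by dose received and the Day 1 and Day 29 results. The subject stays in.
- *Deviation route (SAP 5 and 8.3):* not available for ALT-FLZ-401.
- *Missing-data rule (SAP 7.4.8):* covers values below the quantification limit and otherwise leaves missing data missing. It sets nothing to missing.
- *Early termination (SAP 7.4.7):* if the subject is discontinued under Protocol 5.5, an exit serum is still due. Protocol 6.4 and Table 15.2 footnote g differ on which visit's procedures apply after Day 29, but both include an immunogenicity sample. SAP 7.4.7 then assigns that sample to a scheduled visit.
- *Concomitant medications (SAP 8.4):* tabulated, with no link to SAP 8.6.

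On every route the post-vaccine titer enters the analysis.

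**2. Which visits are exposed?** The only dating input is the ALT-FLZ-401 protocol date of 26 April 2017 (SAP 2). Assume dosing no earlier than that.

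- Day 91 = 26 April + 90 days = 25 July 2017.
- Day 181 = 26 April + 180 days = 23 October 2017; with the 10-day window, 13 October at the earliest.

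The ALT-103-201 protocol version cited in SAP 2 is dated 5 October 2017, and SAP 4 places the change of H1 component at the time of that study. Day 181 can therefore plausibly fall when a new-season vaccine was in use. Day 91 is less exposed if dosing began soon after the protocol date.

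**3. How large could it be?** If m of n subjects have their titer multiplied by k, the mean log titer rises by (m/n) × log k, so the GMT is multiplied by k^(m/n). The GMR changes by the same factor because baseline is unaffected. If only the Fluzone group is affected, the NasoVAX/Fluzone ratio of observed GMTs is multiplied by the reciprocal. With n = 20 and assumed m and k:

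| m | k | Fluzone GMT × | NasoVAX/Fluzone ratio × |
|---|---|---|---|
| 0 | any | 1.00 | 1.00 |
| 1 | 2 | 2^(1/20) = 1.04 | 0.97 |
| 2 | 4 | 4^(2/20) = 1.15 | 0.87 |
| 4 | 8 | 8^(4/20) = 1.52 | 0.66 |

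A true Day 181 GMT of 40 would be observed as 40, 41.4, 45.9 or 60.6 respectively.

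SPR rises by 1/20 = 5 percentage points for each re-vaccinated subject who was below 1:40 and crosses it. A subject already at or above 1:40 adds nothing.

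**The case against.** The strongest reply is that the event may be rare or absent, that the protocol does more than record vaccines, and that analysing every observed titer is a recognised choice.

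- *Protocol 5.5 has two controls.* These are the limit on interfering medications and the joint decision on continuing. That stands, although it is arguable whether either reaches vaccines. Both govern use and participation. Neither says what to do with the data.
- *All-observed analysis.* Legitimate if chosen and stated, but the SAP does not state it, and it answers a different question from persistence after one dose. Vaccines and titers are both listed, and SAP 7.4 permits labelled post-hoc analyses, so affected samples could be found later. A rule fixed in advance is better.
- *Importance.* No stated objective uses the word durability, and the Fluzone comparison is exploratory in SAP 3. This limits the weight of the point without removing it.
- *Intercurrent influenza infection* can also raise titers, and the proposed rule does not address it. That is true.

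A reader might infer more than the documents support:

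- *That Day 91 is equally affected.* For Fluzone it could fall as early as about 25 July 2017, and no availability date for the new vaccine is given.
- *That ALT-103-201 follow-up lay wholly in the 2017-18 season, or that its protocol lets subjects be re-vaccinated freely.* Neither its dosing dates nor its protocol is supplied.
- *That a NasoVAX subject vaccinated late would lose the sera through Day 29.* SAP 5 requires a major deviation affecting the primary immunogenicity outcomes, and SAP 8.3 says only that removal may follow. If one of 15 were removed, 1/15 = 6.7% exceeds the 5% trigger for the ITT analysis, which keeps those sera.
- *That a 4- to 8-fold rise is expected.* The assay is against A/California and the later vaccine carries A/Michigan; the documents give no cross-strain boost.

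**Conclusion.** The gap is real: neither supplied document contains an analysis rule for HAI samples taken after a non-study influenza vaccine, and the visit-wise analysis as written would count them as response to the study dose. The exposure is mainly at Day 181.

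The size is unknown. It is nil if nobody was re-vaccinated. Over the assumed cases shown, the Fluzone GMT is inflated by 4% to 52%. These figures rest on n = 20 analysed subjects, on assumed m and k, and on a uniform fold rise among those re-vaccinated. The timing rests on dosing no earlier than the protocol date.

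The documents do not show that any late result is in fact biased. They show that nothing in the plan would prevent it. The rule should be added.

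**What to change.** Add to SAP 7.4.7 and 8.6, in the same words for both studies and for the PP and ITT populations:

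- Immunogenicity results from samples taken after receipt of a non-study influenza vaccine are set to missing from that date; the subject's earlier samples are retained.
- The number of subjects and samples affected is reported by group and visit.
- A sensitivity analysis includes all samples.

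State in SAP 5 that such a vaccination after Day 29 does not by itself remove a subject from PP.

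One detail needs care. Under SAP 7.4.8, a start date with unknown month in the dosing year is imputed to the dose date, which would wrongly remove every post-dose sample. Partial vaccination dates should be queried or given their own convention.

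The cost is SAP text and one derived flag from vaccine records already planned. No procedure or clinical rule changes. The downside is slightly fewer sera at Days 91 and 181, and the main late-visit estimate then assumes that censored subjects would have resembled those remaining, given group and baseline titer. The sensitivity analysis shows how much the result depends on the censored samples.
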